Study design:	
Randomized Phase 3 global, multi-center, open-label comparison of ipilimumab with and without intratumoral IMO-2125 in subjects with advanced melanoma who had confirmed disease progression while on a PD-1 inhibitor, e.g., nivolumab or pembrolizumab. Subjects will be randomized 1:1 to treatment arms. The primary endpoint family of the study includes ORR and OS.	

Number of subjects (planned): 454

Periodic data reviews will be performed by an Independent Data Monitoring Committee (IDMC) as described in the IDMC Charter. The first IDMC meeting will occur after approximately 20 subjects on each arm have been treated with two doses of ipilimumab. This initial meeting will review safety only.

Inclusion criteria

1. Subjects must be willing and able to sign the informed consent and comply with the study protocol.
2. Must be ≥ 18 years of age.
3. Histologically confirmed metastatic melanoma with measurable (by Response Evaluation Criteria in Solid Tumors [RECIST] v1.1), Stage III (lymph node or in transit lesions) or Stage IVA, IVB, or IVC disease that is accessible for injection. Stage should be determined using the American Joint Committee on Cancer (AJCC) Cancer Staging Manual, Seventh Edition.
4. Confirmed progression during or after treatment with a PD-1 inhibitor (cannot be part of a bi-specific antibody), e.g., nivolumab or pembrolizumab. Confirmed progression is defined as:
 - Radiological progression (confirmed at least 4 weeks after the initial scan showing progressive disease); or
 - For progression based solely on worsening of non-target or new, non-measurable disease, confirmation by an additional scan at least 4 weeks after the initial scan unless progression is accompanied by correlative symptoms.

In addition, all the following must hold:

- No intervening anti-cancer therapy between the last course of PD-1 inhibitor treatment and the first dose of study treatment is allowed except for local measures (e.g., surgical excision or biopsy, focal radiation therapy).
 - The interval between last PD-1 inhibitor and start of study treatment should be at least 21 days with no residual anti-PD-1-related immune toxicities in excess of Grade 1 severity.
 - Subjects who had adjuvant anti-PD-1 treatment are eligible if they have either disease recurrence after the end of adjuvant treatment or on-treatment disease recurrence after ≥ 12 weeks of adjuvant treatment.

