CBC with diff	X	X ⁶	X	X	X		X	X ¹⁴	
Chemistry profile	X	X ⁶	X	X	X		X	X ¹⁴	
CH50/C3/C4		X					X		
Coagulation ⁷		X					X		
Urinalysis		X					X		
Thyroid function tests		X	X	X	X		X	X ¹⁴	
Vital signs ⁸		X	X	X	X	X	X		
ECG		X					X		
Directed physical	X	X	X	X	X	X			
Pregnancy test ⁹	X	X					X		
Ipilimumab dosing		X	X	X	X				
Disease assessment	X					X ¹²		X ¹²	
PRO		X ¹³		X ¹³		X ¹³		X ¹³	
AE/conmeds	Continuous ¹⁰								
Serum samples for anti-drug antibodies ¹⁶		X					X		
Tumor biopsies ¹¹	X ¹¹			X ¹¹					
Telephone contact									X
Anticancer treatment information									X ¹⁵

AE=adverse event; aPTT=activated partial thromboplastin time; C3/C4=complement components C3 and C4; CBC=complete blood count; CH50=total hemolytic complement activity 50; diff=differential; ECG=electrocardiogram; ECOG=Eastern Cooperative Oncology Group; eCRF=electronic case report form; F/up=Follow-up; ICF=informed consent form; INR=international normalized ratio; PK=pharmacokinetic(s); PRO=patient-reported outcome; PT=prothrombin time; TSH=thyroid stimulating hormone; USPI=US Prescribing Information; WOCBP=women of childbearing potential

- All Screening tests and assessments must be performed within 28 days before the date of randomization, except for ECOG and laboratory tests, which should be performed within 10 days before the first dose of study drug, and pregnancy test should be performed within 72 hours, if pregnancy test is not performed within 72 hours prior to randomization, it should be done on the first day of ipilimumab dosing.
- All assessments will occur within a ±3-day window. Ipilimumab dosing should follow the product label (e.g., USPI).
- Subjects who discontinue study treatment due to completion of the planned treatment or for reasons other than disease progression or start of new anticancer treatment will enter the Active Follow-up Period. Assessments during the Active Follow-up Period will follow the schedule of the disease assessments and will occur at Week 12 (±1 week), then every 8 weeks (±2 weeks) for the first year and every 12 weeks (±2 weeks) during subsequent years.
- Subjects who discontinue disease assessments due to either disease progression or the start of new anticancer treatment, with or without disease progression, will enter the Survival Follow-up Period (contacted by telephone every 3 months until death or the end of the study). Assessments will occur within a ±14-day window.

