- Subjects must be randomized within 28 days after signing the ICF; the first dose of study drug should be administered within 2 days after randomization.
- CBC and chemistries do not have to be repeated if Screening tests are completed within 7 days of start of treatment.
- PT, aPTT, INR.

8. Vital signs will include systolic and diastolic blood pressure, body temperature, pulse rate, body weight, and height (Week 1 only). Vital signs should be completed prior to treatment administration.
9. WOCBP only. Pregnancy test after randomization should be completed as deemed necessary by the Investigator or required by local law.
10. During the Follow-up Periods, for 90 days after the last dose of study treatment, all SAEs, irAEs, AEs Grade ≥ 3 , and associated concomitant medications for their treatment must be reported. For the remainder of the Follow-up Periods, AE reporting should be limited to Treatment-related Grade ≥ 3 AEs and SAEs, and the associated concomitant medications.
11. Optional (see Laboratory Manual).
12. To inform treatment management decisions, disease assessments are to be completed at Week 12 (± 1 week), then every 8 weeks (± 2 weeks) for the first year and every 12 weeks (± 2 weeks) during subsequent years.
13. To minimize bias in the PRO data, disease and PRO assessments are to be completed prior to study drug administration and AE evaluations at Weeks 1, 7, and 12 (± 1 week), then every 8 weeks (± 2 weeks) for the first year and every 12 weeks (± 2 weeks) during subsequent years.
14. Per institutional practices following the frequency of active follow-up disease assessments.
15. Follow-on anticancer treatment information will be collected during the telephone calls.
16. Serum samples will be collected for analysis of anti- ipilimumab antibodies; details are provided in the Laboratory Manual. Baseline sample to be collected at Week 1 before the first dose of study treatment.

Table 2: Schedule of Evaluations – Ipilimumab with IMO-2125 (Arm B)

Evaluation	Screening ¹	Combination Treatment ²							IMO Maintenance			Active F/up ³	Survival F/up ⁴
	Week	1	2	3	5	8	11	12	16	20	24		
Informed consent ⁵	X												
Inclusion/Exclusion	X												
Medical History	X												
ECOG	X	X			X	X	X		X	X	X		
CBC with diff	X	X ⁶	X	X	X	X	X		X	X	X	X ¹⁸	
Chemistry profile	X	X ⁶			X	X	X		X			X ¹⁸	
CH50/C3/C4 ⁷		X					X						
Coagulation ⁸		X							X				
Urinalysis		X							X				
Thyroid function tests		X			X	X	X		X			X ¹⁸	

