5. Subjects must be randomized within 28 days after signing the ICF; the first dose of study drug should be administered within 2 days after randomization.
6. CBC and chemistries do not have to be repeated if Screening tests are completed within 7 days of start of treatment.
7. Samples will be collected pre-dose, and at 1, 2 and 4 hours (± 10 minutes) post-dose.
8. PT, aPTT, INR.
9. Vital signs will include systolic and diastolic blood pressure, body temperature, pulse rate, body weight, and height (Week 1 only). Vital signs should be completed prior to treatment administration.
10. WOCBP only. Pregnancy test after randomization should be completed as deemed necessary by the Investigator or required by local law.
11. IMO-2125 should be administered prior to ipilimumab.
12. During the IMO Maintenance Period, all CTCAE Grade ≥ 2 irAEs and laboratory abnormalities (regardless of relationship to study drug) should be monitored until resolution, stabilization, or return to baseline. During the Follow-up Periods, for 90 days after the last dose of study treatment, all SAEs, irAEs, AEs Grade ≥ 3 , and associated concomitant medications for their treatment must be reported. For the remainder of the Follow-up Periods, AE reporting should be limited to Treatment-related Grade ≥ 3 AEs and SAEs, and the associated concomitant medications.
13. Blood samples for evaluation of plasma IMO-2125 concentrations will be collected pre-dose and at 1, 2, and 4 h post-dose (± 30 minutes) at Week 1 and Week 11 only.
14. Serum samples will be collected for analysis of anti-IMO-2125 and anti-ipilimumab antibodies; details are provided in the Laboratory Manual. Baseline sample to be collected at Week 1 before the first dose of study treatment.
15. Optional (see Laboratory Manual).
16. To inform treatment management decisions, disease assessments are to be completed at Week 12 (± 1 week), then every 8 weeks (± 2 weeks) for the first year and every 12 weeks (± 2 weeks) during subsequent years.
17. To minimize bias in the PRO data, disease and PRO assessments are to be completed prior to study drug administration and AE evaluations at Weeks 1, 8, and 12 (± 1 week), then every 8 weeks (± 2 weeks) for the first year and every 12 weeks (± 2 weeks) during subsequent years.
18. Per institutional practices following the frequency of active follow-up disease assessments.

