#### **4.4 RANDOMIZATION PROCEDURES AND BLINDING**

This is an open-label trial. Randomization will use a central Interactive Response Technology (IRT) system. Subjects will be randomized in blocks of a 1:1 ratio to either ipilimumab with IMO-2125 or ipilimumab alone. Randomization is stratified by the duration of prior anti-PD-1 therapy ( $\geq 12$  weeks vs  $< 12$  weeks), metastasis stage (M1c vs other) and BRAF mutation (BRAF wild type vs BRAF mutation positive with prior targeted therapy vs BRAF mutation positive without prior targeted therapy). Despite this being an open label trial, the sponsor will make every effort to maintain the integrity of the trial by avoiding review of aggregated efficacy results by treatment arm during the course of the trial.

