### **8.2.5 Baseline Definition**

Baseline is defined as the most recent, non-missing value prior to the first study treatment dose date and time. For enrolled subjects who did not receive study treatment during the study, baseline is defined as the latest, non-missing collected value before the date of randomization.

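### The baseline QLQ-C30 is scheduled at Week 1 with no rule that it precede open-label randomization, so the score from which all change is measured can be given after the arm is known

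*Protocol*

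**What the plan says.** Both schedules of evaluations (Protocol Tables 1 and 2, repeated in SAP 16.1) leave the Screening cell of the PRO row empty. In Arm A (Table 1, footnote 13) the questionnaire is to be "completed prior to study drug administration and AE evaluations at Weeks 1, 7, and 12", and in Arm B (Table 2, footnote 17) "completed prior to study drug administration and AE evaluations at Weeks 1, 8, and 12". Both footnotes open with the aim of limiting bias: "To minimize bias in the PRO data, disease and PRO assessments are to be completed prior to study drug administration and AE evaluations". Protocol 11.2 repeats the ordering before drug and AE assessment. None of these places mentions randomization or disclosure of the arm.

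On timing, footnote 5 of both tables says that "the first dose of study drug should be administered within 2 days after randomization". The design is an "open-label comparison of ipilimumab with and without intratumoral IMO-2125", and SAP 4.4 confirms: "This is an open-label trial".

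SAP 8.2.5 takes the last non-missing value before the first dose as baseline. For subjects never treated, "baseline is defined as the latest, non-missing collected value before the date of randomization". SAP 13.2 summarizes change from baseline by visit. SAP 13.3 models that change with the baseline score as a covariate and reports arm differences with 95% confidence intervals at each visit. SAP 13.4 summarizes the same change by responder status. The introduction to SAP 13 makes all of this descriptive, without p-values, in the ITT set.

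**The concern.** The footnotes guard the questionnaire against two influences, the dose and the AE interview. They do not guard it against a third: in an open-label trial, subjects may answer differently once they know their arm. The arms differ visibly from the first treatment (an infusion in Arm A, an injection into a selected lesion in Arm B), and Arm A subjects may not cross over. A subject completing the form on the dosing day would therefore normally know the allocation.

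A baseline given after disclosure is a post-randomization measurement. Randomization no longer guarantees that it is balanced between arms, and both subtracting it and adjusting for it carry any imbalance due to disclosure into the estimated arm difference. At stake is the reading of the QLQ-C30 change scores, a named secondary endpoint.

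**Working it through.** **Sequence.** Nothing is scheduled at Screening. Randomization comes next, then the first dose within 2 days, and the only form before that dose is the one at Week 1. For treated subjects SAP 8.2.5 therefore selects the Week 1 form. For never-treated subjects it asks for a value from before randomization, where no form is scheduled.

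**Bias formulas.** The plan gives no figure to reproduce. Let X be the baseline and Y the follow-up score, and let b be the within-arm slope of Y on X. Suppose that learning the allocation shifts Arm A's baseline by d and that a fraction p of this shift remains at later visits. A uniform shift leaves b unchanged.

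- Difference in raw change, (Y_B − X_B) − (Y_A − X_A): moves by d − p × d = (1 − p) × d.
- Baseline-adjusted difference, (Y_B − Y_A) − b × (X_B − X_A): moves by b × d − p × d = (b − p) × d. Modelling change instead of Y, as SAP 13.3 does, gives the same adjusted difference when baseline is a covariate.
- With a baseline taken before randomization, X does not move and both differences move by −p × d.

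**Illustration.** The documents give neither d nor b. Assume d of 2 to 5 points on the 0 to 100 scale and b of 0.4 to 0.7. Absolute sizes in points:

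| Case | Raw change, Week 1 baseline | Adjusted, Week 1 baseline | Either analysis, pre-randomization baseline |
|---|---|---|---|
| Shift at baseline only (p = 0) | d = 2 to 5 | b × d: 0.4 × 2 = 0.8 to 0.7 × 5 = 3.5 | 0 |
| Shift fully persists (p = 1) | 0 | (1 − b) × d: 0.3 × 2 = 0.6 to 0.6 × 5 = 3.0 | d = 2 to 5 |

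For a given d, the adjusted bias has opposite signs in the two rows (+b × d against −(1 − b) × d). For example, if Arm A subjects score lower on a functional scale only at baseline, their later change looks better and the bias runs against the combination. If the lower scoring persists, the adjusted bias runs in its favour.

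**The case against.** **Knowledge of the arm is inferred.** A reader might conclude that every subject gives the baseline knowing the arm. The documents do not support that, because they never say when subjects are told. Randomization and first dose may fall on the same day, and Table 1 adds that "All assessments will occur within a ±3-day window" (Table 2 has the same window), so a site could collect the form earlier. This stands, and it limits the claim to a missing ordering rule. But nothing requires the earlier form.

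**The bias may be smaller, or the fix no improvement.** A reader might also take b × d as the bias at every visit. That holds only if the shift is confined to baseline. Subjects know their arm at all later visits too; if the shift persists in full, raw change from Week 1 cancels it, while a pre-randomization baseline leaves all of d. This stands as a caution on size. The reason for moving the form is not a guaranteed smaller number. It is that the baseline can then not depend on allocation. What remains is open-label reporting at follow-up, a familiar limitation that can be stated plainly.

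**The endpoint is descriptive.** There are no tests and no alpha is allocated (SAP 7.2 and 13), so only interpretation is affected. Even so, the point and interval estimates are the PRO result that will be read.

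**It is late, and a strict redefinition would do harm.** SAP 8.2.10 says the distribution over randomization strata was already known when the SAP was finalized, so enrolment may be well advanced. If only pre-randomization forms counted as baseline, subjects with just a Week 1 form would have none; SAP 8.2.6 then sets change to missing and SAP 8.1.1 does not impute PRO data. This stands, and the fix below allows for it.

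**Untreated subjects.** SAP 8.2.5 is a general rule for all measures. The mismatch for the QLQ-C30 matters only for never-treated subjects who also have later forms. Neither their number nor such data is given, so it is a minor point.

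**Conclusion.** The concern holds as a gap in the plan. The baseline QLQ-C30 can be, and usually would be, completed after the allocation is known, and every change analysis depends on it. Arm differences in change can be biased; the documents do not establish that they are, by how much, or toward which arm. On the assumed d of 2 to 5 points and b of 0.4 to 0.7, the bias in the adjusted difference is 0.8 to 3.5 points if only the baseline shifts and 0.6 to 3.0 points with the opposite sign if the shift persists. In raw change it is 2 to 5 points or 0. These ranges rest entirely on the assumed inputs. ORR, OS and type I error are untouched. The gap is worth closing because closing it is cheap, not because it threatens the trial's main conclusions.

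**What to change.** 1. **Schedule, for subjects still to be randomized.** Amend the PRO row and footnotes 13 and 17 of Protocol Tables 1 and 2 (and SAP 16.1) so that the baseline QLQ-C30 is completed after consent and before randomization, as close to it as practical. Screening can run to 28 days, and an early form would be a poorer baseline.
2. **SAP 8.2.5.** For PRO, define baseline as the last form before randomization if there is one, otherwise the last pre-dose form. No enrolled subject then loses a baseline. Apply the same order to never-treated subjects, so that a Week 1 form can serve if it is all they have.
3. **Reporting.** Flag each baseline form as dated before, on or after the day of randomization, and tabulate the counts and the baseline scores by arm. A large imbalance would be visible, though it could not be separated from chance. State the limitation beside the PRO results.

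The cost is small: each randomized subject completes the same number of questionnaires, the ePRO device must be set up before randomization, and a few screen failures will also complete a form. If enrolment is already complete, items 2 and 3 still apply and need no new data.

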4.3.1.2. Nonclinical Toxicology

General toxicology studies were conducted in rats and monkeys administered IMO-2125 by s.c. injection once weekly for 4 and 13 consecutive weeks. Findings in these studies were consistent with immune stimulation, the proposed mechanism of action (Investigator's Brochure).

In chronic twice-weekly administration toxicity studies (26 weeks in rats and 39 weeks in monkeys), findings in the liver (rats) and kidney (monkey) were similar to what has been noted with other oligonucleotides (Investigator's Brochure). Monitoring for these potential effects is included in the ongoing and planned clinical studies using standard safety parameters for liver and kidney function. In addition, lymphomas and leukemias that likely were secondary to chronic immune stimulation and sarcomas at the site of injection that were likely secondary to chronic irritation/inflammation at the injection sites were noted in rats (Investigator's Brochure). Similar findings were not noted in monkeys (Investigator's Brochure).

Due to substantial differences in the pattern of TLR expression in rodents when compared with non-human primates and humans, the pharmacodynamic effects of chronic TLR9 stimulation in cynomolgus monkey may be more representative of the anticipated effects in humans than the effects seen in rodents.

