The Phase 3 regimen adds maintenance doses of IMO-2125 at 16, 20, and 24 weeks following completion of combination therapy. Prolonging the duration of IMO-2125 therapy provides continued innate immune stimulation in response to neoantigens that may emerge in response to treatment ([Schumacher and Schreiber, 2015](#)). Safety follow-up to support this longer dosing period is now available for several 2125-204 study subjects and, along with pre-clinical toxicology assessment of 6 month continued dosing, does not suggest a risk for cumulative toxicity from these additional maintenance doses. Study 2125-204 has recently been amended to assess dosing through 29 weeks; longer-term administration of IMO-2125 (approximately one year) is being evaluated in Study 2125-RST-101. Refer to the Investigator's Brochure for the most updated safety information.

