9.3.3. Administration

Subjects will be randomized (1:1) to receive either:

1. Arm A – ipilimumab 3 mg/kg i.v. at Weeks 1, 4, 7, and 10
or
2. Arm B – IMO-2125, 8 mg intratumorally at Weeks 1, 2, 3, 5, 8, 11, 16, 20, and 24 in combination with ipilimumab 3 mg/kg i.v. at Weeks 2, 5, 8, and 11

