9.3.4. Dose Modification

The most common AEs following intratumoral administration of IMO-2125 have been non-specific “flu-like” symptoms and mild to moderate injection site reactions. In combination with ipilimumab, IMO-2125 has been associated with irAEs (Section 10.1.3.4) and fever. Ipilimumab dosing will follow the local package insert. IMO-2125 therapy should be continued if ipilimumab is discontinued early for toxicity.

Dose modification instructions for IMO-2125 including its use in combination with ipilimumab are provided in [Table 3](#).

Table 3: Dose Modification Instructions for IMO-2125

Event	Action	Dose Modification
Local or mild systemic reaction (e.g., pyrexia)	Supportive measures as required. Continue treatment with IMO-2125 per clinical discretion.	None
Severe systemic reaction for which more aggressive measures including hospitalization are required (e.g., severe hypotension)	Supportive measures as required. Hold further dosing until the event resolves to baseline or Grade 1 and the re-treatment criteria below are met.	None.
Life-threatening AE (e.g., anaphylaxis)	Supportive measures as required.	Discontinue treatment
Serious procedural complication related to deep or visceral injection (e.g. pneumothorax or hematoma formation)	Supportive measures as required	Discontinue visceral injections (treatment may be continued if a superficial lesion or tumor-involved lymph node is available for injection instead)

Conventional supportive medications (including infliximab for immune-related colitis and growth factor support) are permitted.

Criteria for re-initiation of treatment with each dose of study drug include:

- ANC $\geq 1.5 \times 10^9/L$ (1500/ μL);
- Platelets $\geq 75 \times 10^9/L$ (75,000/ μL);
- Resolution of all clinically significant non-hematologic toxicities for which a causal association to study treatment cannot be ruled out to Grade ≤ 1 or baseline.

If the subject does not meet these criteria, dosing will be delayed, and the subject should be re-evaluated within 48 to 72 hours. If the next dose is delayed by more than 21 days for toxicity, the subject should be removed from study treatment unless approved by the medical monitor.

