Hematology and chemistry laboratory tests will be summarized using shift tables by treatment arm. Subjects must have a baseline and at least one non-missing post-baseline assessment to be included in the shift analysis.

Summaries of shifts from baseline will be provided for hematology and chemistry laboratory tests that are graded by CTCAE v4.03 ([Appendix Section 16.5](#)). This shift table will include a worst-case (defined as the highest CTCAE grade) post-baseline summary that includes data from both scheduled and unscheduled visits. Categories based on value ranges for CTCAE grades will be shown for baseline and worst case post-baseline, with the number and percentage of subjects in each.

Summaries of shifts from baseline with respect to the normal range will be provided for the following laboratory parameters: WBC, RBC, hematocrit, platelet count, neutrophils, lymphocytes, total bilirubin, creatinine, LDH, ALT, AST, and TSH. This shift table will include both shift to lowest and shift to highest post-baseline with respect to the normal range. All data from both scheduled and unscheduled visits will be considered for the shifts. Categories of normal range, below the normal range, and above the normal range will be shown for baseline, the highest and the lowest post-baseline, with the number and percentage of subjects in each. A figure showing the mean, median, quartiles, range, and outliers beyond the interquartile range (boxplot) for each treatment arm at each scheduled visit will be produced for hematology and chemistry parameters. It will have the nominal visit assessment week on the horizontal axis and the parameter value on the vertical axis. The number of subjects assessed in each treatment arm will be displayed below each visit.

A paneled scatterplot of the ratio of maximum total liver function tests to ULN versus baseline liver function tests to ULN will be produced by treatment arm. The liver function tests included in the plot are ALT, AST, total bilirubin, and alkaline phosphatase.

Listing of all laboratory values will be provided with the CTCAE v4.03 grade (if applicable) and laboratory values LLN and ULN will be flagged.

Summaries to be produced are:

- Summary of Change from Baseline in Hematology
- Summary of Change from Baseline in Chemistry
- Summary of Change from Baseline in Coagulation
- Summary of Change from Baseline in Complement
- CTCAE Shifts from Baseline Grade in Hematology

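### Arm B has no scheduled chemistry or thyroid test between Week 16 and Active Follow-up, although IMO-2125 is given at Weeks 20 and 24

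*Protocol*

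**What the plan says.** Protocol Section 9.3.3 gives Arm B "IMO-2125, 8 mg intratumorally at Weeks 1, 2, 3, 5, 8, 11, 16, 20, and 24". Section 4.4.4 explains the last three doses: "The Phase 3 regimen adds maintenance doses of IMO-2125 at 16, 20, and 24 weeks following completion of combination therapy".

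In Protocol Table 2 the Arm B chemistry and thyroid rows are marked at Weeks 1, 5, 8, 11 and 16 (chemistry also at Screening), and then only in the Active Follow-up column. The CBC, vital signs and ECOG rows are marked at Weeks 16, 20 and 24. Footnote 18 governs the follow-up tests: "Per institutional practices following the frequency of active follow-up disease assessments".

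Three other places bear on laboratory monitoring in this period:

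- Section 4.3.1.2, after reporting liver findings in rats and kidney findings in monkeys on chronic dosing: "Monitoring for these potential effects is included in the ongoing and planned clinical studies using standard safety parameters for liver and kidney function".
- Section 9.3.4, among the criteria applied to each dose of study drug: "Resolution of all clinically significant non-hematologic toxicities for which a causal association to study treatment cannot be ruled out" (to Grade 1 or less, or baseline).
- Table 2 footnote 12 and Section 10.1.3.9, which require laboratory abnormalities of Grade 2 or higher in the IMO Maintenance Period to be followed until they resolve, stabilize or return to baseline.

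For the CTCAE chemistry shifts, SAP 11.8 says: "Categories based on value ranges for CTCAE grades will be shown for baseline and worst case post-baseline". It also plans normal-range shifts, by-visit summaries and boxplots, and a plot of maximum liver tests, all by arm.

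**The concern.** The maintenance doses are new in this Phase 3 regimen, and the protocol says liver and kidney function are watched. Yet routine chemistry and thyroid testing stops at the first of the three maintenance visits while dosing goes on. A hepatic, renal or thyroid change that arises after Week 16 and settles before follow-up would be recorded only if a site chose to test. The laboratory tables are descriptive and do not touch the primary endpoints, but they are the organ-function evidence for the maintenance doses, and nothing in SAP 11.8 tells a reader that scheduled testing was interrupted.

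**Working it through.** No figure in the plan is at issue, so the check consists of reading the two schedules and counting.

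| Row | Arm A (Table 1) | Arm B (Table 2) |
|---|---|---|
| Chemistry | Screening, 1, 4, 7, 10, 14, Active Follow-up | Screening, 1, 5, 8, 11, 16, Active Follow-up |
| Thyroid | 1, 4, 7, 10, 14, Active Follow-up | 1, 5, 8, 11, 16, Active Follow-up |
| IMO-2125 | none | 1, 2, 3, 5, 8, 11, 16, 20, 24 |
| Ipilimumab | 1, 4, 7, 10 | 2, 5, 8, 11 |

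**Is the gap real?** In the same table the Arm B CBC row is filled at Weeks 16, 20 and 24, and SAP 16.1 Table 3 shows the same blanks for chemistry and thyroid. The empty cells are therefore not a fault of text extraction.

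**Maintenance visits covered.** 1 of 3: Week 16 has both tests, Weeks 20 and 24 have neither.

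**Doses after the last scheduled on-treatment test.** Weeks 20 and 24, so 2/9 = 22%. If the Week 16 sample is taken before that day's injection, which the documents do not state, Week 16 is added: 3/9 = 33%.

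**Share of the dosing span.** (24 − 16)/(24 − 1) = 8/23 = 35% of the time from first to last dose lies after the last scheduled on-treatment test.

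**Next scheduled test.** Active Follow-up uses the disease-assessment grid: Week 12, then every 8 weeks, so 20, 28 and so on. The first grid point after Week 24 is Week 28.

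- Week 16 to Week 28: 12 weeks = 84 days. With the ±3-day treatment window and the ±14-day follow-up window, 84 ± 17 gives 67 to 101 days.
- Last dose to Week 28: 4 weeks = 28 days, and 28 ± 17 gives 11 to 45 days.

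**Who has no later scheduled test.** Table 2 footnote 4 moves subjects who stop disease assessments for progression or new anticancer treatment to Survival Follow-up, which is by telephone. If that happens after Week 16, no further chemistry or thyroid test is scheduled for them.

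**What enters each SAP display.**

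- By-visit summaries and boxplots: planned visits only. SAP 7 and 8.2.9 keep unscheduled values out of everything except worst-case summaries. There are therefore no planned Arm B values at Weeks 20 and 24.
- CTCAE shifts and normal-range shifts (the latter include bilirubin, creatinine, ALT, AST and TSH): scheduled and unscheduled values. Protocol 16.2 collects laboratory data through Active Follow-up, so later values can enter if a sample was drawn.
- Liver-test plot: on-study maximum, so again later values can enter.
- Inclusion in the shift tables needs a baseline and one post-baseline value. A subject last tested at Week 11 or 16 therefore counts the same as one tested throughout.

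**The case against.** The other side has good points, and several of them limit the finding.

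- A reader might infer that the laboratory tables miss the maintenance period. They do not. Week 16 is itself a maintenance visit with both tests, and the shift tables and liver plot accept unscheduled and follow-up values.
- A reader might infer a bias in favour of IMO-2125. The documents do not show one. Each arm has four scheduled post-baseline tests in its treatment period, and Arm B's run later. The Week 20 chemistry that an Arm A subject in Active Follow-up might have rests on Table 1 footnote 14, which carries the same institutional-practice wording as footnote 18. Arm B subjects are also on site at Weeks 20 and 24, where extra tests can be drawn.
- A reader might infer that the dosing criteria cannot be checked at Weeks 20 and 24. That is too strong. Footnote 12 requires follow-up of known abnormalities, Section 10.1.3.8 lets investigators order supplemental tests, and clinically significant results are reported as adverse events. What is missing is scheduled data to find a new abnormality.
- The animal findings came from twice-weekly dosing for 26 and 39 weeks, whereas maintenance here is three doses four weeks apart. Section 4.4.4 judges that these doses do not suggest cumulative toxicity. The clinical risk that Section 9.3.4.3 ties to duration is thrombocytopenia, for which CBC is kept at every maintenance visit.
- SAP 11.8 already prints the number assessed under each boxplot visit and uses non-missing denominators.

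These points reduce the size of the problem but do not fill the two blank visits. Safety nets that respond to a known or symptomatic event do not replace a scheduled sample. The count under a boxplot also does not explain why the worst-case tables are thin after Week 16.

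**Conclusion.** The point holds in limited form. Arm B has no scheduled chemistry or thyroid test from Week 16 until about Week 28, a nominal 12 weeks (67 to 101 days with windows) for a subject who completes treatment. At least 2 of 9 IMO-2125 doses, and 3 of 9 if the Week 16 sample is pre-dose, follow the last scheduled on-treatment test. By-visit displays lack Weeks 20 and 24. Worst-case displays cover that period only as far as sites chose to test, so they may under-ascertain late or transient changes. Neither the direction nor the size of any between-arm bias can be established. The documents do not say how many subjects reach Weeks 20 and 24, or how often sites test outside the schedule.

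The main evidence is the blank cells in Table 2. Footnote 18 matters only because it makes the next test depend on local practice. The Week 28 figure assumes the subject completes treatment without progression or new therapy. Those blanks sit uneasily with Section 4.3.1.2, Section 9.3.4, and footnote 12 with Section 10.1.3.9, and the sponsor should resolve this.

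**What to change.** **Protocol.** The sponsor should reconcile the Arm B chemistry and thyroid rows of Table 2 (and SAP 16.1 Table 3) with footnote 12 and Section 10.1.3.9, with Section 4.3.1.2, and with the Section 9.3.4 criteria for each dose. No testing schedule is proposed here.

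**SAP 11.8.** Keep the planned worst-case tables as they are and add:

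1. A by-arm chemistry and thyroid shift summary through Week 16, where scheduled testing is comparable (Arm A Weeks 4, 7, 10 and 14; Arm B Weeks 5, 8, 11 and 16).
2. Arm B chemistry and thyroid results after Week 16, with the number of subjects actually tested.
3. A footnote on the affected tables and figures stating that these tests were not scheduled at Weeks 20 and 24 in Arm B.

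The summary in item 1 must supplement the full worst-case tables and not replace them: on its own it would discard the late unscheduled and follow-up values that matter most here.

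**Cost.** SAP wording and a few extra descriptive outputs from data already collected. No effect on the primary endpoints or on Type I error.
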